1 INTRODUCTION

This document is a protocol for a clinical research study sponsored by Masimo Corporation. The study will be conducted in compliance with the ethical principles that have their origin in the Declaration of Helsinki. In participating in the study, the Investigator agrees to adhere to all stipulations of this protocol, the conditions of IRB/IEC approval, 21 CFR 50, 21 CFR 56, 21 CFR 812, ISO-14155, and International Conference on Harmonization Good Clinical Practice guidelines ICH GCP.

1.1 Background and Rationale

Masimo Corporation is the developer of noninvasive technologies for the measurement and monitoring of physiological variables, such as arterial oxygen saturation (SpO₂), total hemoglobin concentration (SpHb), carboxyhemoglobin concentration (SpCO), methemoglobin concentration (SpMet), acoustic respiration rate monitoring (RAM), End tidal CO₂ (EtCO₂), and other physiological parameters.

Assessment of blood pressure is vital in clinical practice. In hospitalized patients, blood pressure measurements are obtained as frequently as every day or prior to and during medical procedures. In outpatient clinic settings, blood pressure measurements are taken as part of routine physical examination, and also in the follow-up of known patients with high blood pressure for appropriate management. High blood pressure is one of the most chronic conditions that affects a large population in the United States, and a lack of adequate detection and management of high blood pressure may lead to coronary heart disease, stroke, heart failure etc. (Ventura and Lavie, 2018). Hypotension is associated with increased risk of falls, dementia, cardiovascular disease, syncope and mortality if left untreated (P&T 2019). Since both hypertension and hypotension can impair the function of vital organs such as the heart, brain, or kidneys, arterial blood pressure monitoring, is a mainstay of hemodynamic monitoring and is an important indicator of a person's state of health (Meidert & Saugel, 2018). The gold standard for measurement of arterial pressure is through direct arterial measurement using a catheter (Sahu & Bhaskaran, 2010). This technique is commonly performed during high-risk surgeries and in intensive care medicine; however, this technique is neither practical nor appropriate for non-hospitalized patients or asymptomatic individuals (Meidert & Saugel, 2018).

For these reasons, blood pressure is commonly measured noninvasively. The standard noninvasive method for blood pressure measurement is the auscultatory technique using an arm cuff, stethoscope, and a manometer. Blood pressure measurement is performed by placing the stethoscope over the brachial artery and then inflating the arm rubber cuff to a level higher than the systolic pressure. The cuff is then gradually deflated and blood pressure is noted when Korotkoff sounds are heard. Korotkoff sounds are the audible turbulent sounds of the blood in the brachial artery when blood flow is constricted. Traditionally, the systolic blood pressure is taken to be the pressure at which the Korotkoff sound is first heard and the diastolic blood pressure is the pressure at which the Korotkoff sound is just barely audible or when it becomes silent.

An alternative method to the auscultatory method is the oscillometric method. The term NIBP, for Non-Invasive Blood Pressure, is often used to describe oscillometric monitoring equipment (Sandham, n.d.). The equipment is functionally similar to that of the auscultatory method, but with an electronic pressure sensor fitted in to detect blood flow, instead of using the stethoscope and the clinician's ear (Sandham, n.d.). These devices automatically inflate the cuff pressures above systolic pressure and then deflate at a controlled rate. A proprietary algorithm is

then used to calculate the systolic and diastolic pressure. Masimo is currently developing a device for the noninvasive measurement of blood pressure that can be used by clinicians to assess patient physical status.

1.2 Investigational Devices

Masimo automated non-invasive blood pressure (NIBP) device

The device is not FDA-cleared and is considered investigational. The investigational device will undergo risk analysis and safety testing in accordance with applicable safety standards, including electrical safety, current leakage, mechanical safety and biocompatibility testing for patient contacting materials, prior to use in the study.

Laptop with data collection software

1.3 Risk/Benefits

Benefits: There is no direct benefit to the individual for participation in this research study. Future benefits might include a development of a noninvasive blood pressure device that can accurately estimate a person's blood pressure.

Risks: There is a potential for the blood pressure cuff to become over-pressurized during automated blood pressure measurement. The excess pressure on the skin tissue could potentially lead to skin injury, i.e. necrosis. To mitigate this risk, the system is designed with [REDACTED]

[REDACTED] The measurement will be monitored by a healthcare professional during the course of the study who will be trained and instructed to remove the cuff if the subject experiences any discomfort.

There is a risk of electric shock if defibrillation is performed while the subject is wearing the device. To minimize this risk, the device should be removed if the subject will undergo defibrillation.

2 STUDY OBJECTIVES

The objective of this study is to evaluate the clinical performance of a digital noninvasive blood pressure measurement device. The noninvasive blood pressure measurements will be compared to reference auscultatory measurements. The difference will be expressed in terms of mean and standard deviation.

3 STUDY DESIGN

This is a prospective, nonrandomized multi-center study, which is based on the ISO standard 81060-2:2018 for the investigation of noninvasive sphygmomanometers.

The study will be conducted at two sites where noninvasive blood pressure measurements will be [REDACTED]

[REDACTED]
[REDACTED]

The study will be conducted [REDACTED] to meet the blood pressure distribution requirements and the limb size distribution requirements in the ISO 81060-2:2018.

[REDACTED] Site 1 [REDACTED] will enroll [REDACTED] patients from among the physician's patients. Site 2 [REDACTED] volunteers.

[figure not shown]

Figure 4: Blood pressure distribution (ISO 81060-2:2018)

Stage 2 will begin after the minimum subjects have been enrolled in the study to meet the blood pressure distribution requirements. Stage 2 will satisfy the cuff distribution requirements of ISO 81060-2:2018. Each cuff size will be tested as per requirements of ISO 81060-2:2018.

Cuff size	Upper half of range of cuff size	Lower half of range of cuff size
Small, Medium, Large	40% of subjects	40% of subjects

Figure 5: Cuff size distribution (ISO 81060-2:2018)

Blood pressure measurements will be obtained using the Masimo NIBP device and also obtained using the auscultatory method as a reference. Each value from the Masimo device will be paired with two measurements from two observers using the reference auscultatory technique, for a total of 4 successful paired measurements per subject. A pair is considered valid if both observers' SBP and DBP readings are within 4 mmHg and the prototype successfully measures.

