5 SUBJECT SELECTION AND WITHDRAWAL

5.1 Number of Subjects

A minimum of 85 subjects with diversified demographics (i.e. age, gender, ethnicity, comorbidities etc.) will be enrolled.

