5.2 Inclusion Criteria

- Age 18 years and older
- Site 1; Stage 1 only: Subjects with a history of hypertension ($> 140/85$ mmHg) or hypotension ($\leq 100/60$ mmHg) within the last 3 months. Stage 2 only: No criterion for blood pressure
- Site 2; Stage 1 and 2: Subjects with systolic blood pressure $< 140/90$ mmHg.
- Ability to provide informed consent

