7 OVERALL STUDY PROCEDURES

7.1 Informed Consent and Screening Procedure

7.1.1 Full written informed consent will be obtained for all subjects prior to enrollment in the study.

7.1.2 During the COVID19 pandemic, subjects will be asked to wear a face mask when they arrive at the research site.

7.1.3 In Stage 1, a screening blood pressure measurement will be taken for all consented subjects during the day of data collection. Subjects must meet the blood pressure requirements in order to be enrolled in the study. Subjects with screening blood pressure outside the Stage 1 values will be removed from the study as screen failures.

Screening Blood Pressure Values		
	Systolic	Diastolic
Hypertensive	> 140 mmHg	> 85mmHg
Hypotensive	< 100 mmHg	< 60 mmHg

7.1.4 In Stage 2, screening procedures for subjects will include a measurement of subjects' upper arm circumference. Subjects will be categorized into bins for the Masimo blood pressure cuff used, according to the table below. The Masimo blood pressure cuff sizes are: Small (20-26 cm), Medium (25-34 cm) and Large (32-43 cm).

	Small		Medium		Large	
Upper Arm Circumference	20-23 cm	23-26 cm	25-29.5 cm	29.5-34 cm	32-37.5 cm	37.5-43 cm

- Subjects may be removed from the study as screen failures if their arm circumference falls into a bin that has had sufficient enrollment.

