7.2 Study Procedure

7.2.1 Ensure the subject is in a relaxed and comfortable position, either seated or lying down, with the arm at heart level and legs uncrossed. Subject should be in the same position for at least 5 minutes prior to blood pressure measurement. During that time, subject demographics and health history may be completed in the CRF.

7.2.2 [REDACTED].

7.2.3 Measure arm circumference and place the appropriate size cuff preferably on the left arm of the subject. The middle of the cuff should be at same level as the heart, see Figure 8. Do not place cuff on an extremity selected for IV infusions or any other intravascular access, e.g. dialysis.

7.2.4 Perform an auscultatory measurement. See section 7.3 for details on the auscultatory measurement procedure (reading R_0 in Figure 7).

7.2.5 Wait at least 60 seconds to allow venous blood flow to normalize.

7.2.6 [REDACTED].

7.2.7 Perform [REDACTED] blood pressure measurement procedure (T_0 in Figure 7).

7.2.8 Wait at least 60 seconds to allow venous blood flow to normalize.

7.2.9 Remove the Masimo cuff and automated blood pressure device and replace with the reference auscultatory cuff and stethoscope.

7.2.10 Perform an auscultatory measurement (R_1 in Figure 7).

7.2.11 Repeat 7.2.5-7.2.10 until at least four valid automated and auscultatory measurement pairs have been performed or eight measurement pairs have been attempted.

- A measurement pair is considered valid if the observer difference criteria in 7.3.4 is satisfied and the automated blood pressure device performs a successful measurement.
- Counting begins with measurement pair T_0-R_1 (e.g. $T_0-R_1, T_1-R_2, T_2-R_3 \dots$ maximum up to T_7-R_8 . See Figure 7).

7.2.12 If less than four paired measurements are obtained after eight paired attempts, subject participation in the study will end.

7.2.13 Be sure to check cuff site health and integrity between measurements.

7.2.14 Disinfect auscultatory blood pressure cuff and allow to air dry, per manufacturer's cleaning directions, after use with each patient.

7.2.15 No treatment decisions will be made based on blood pressure results from study devices.

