10.3 Case Report Forms

The Sponsor shall provide a paper Case Report Form (CRF) template to the site. The site shall capture study data in the CRFs for each subject enrolled. The CRFs will be completed and signed by principal investigator. This also applies to those subjects who fail to complete the study. If a subject withdraws from the study, the reason must be noted on the CRF. Case report forms are to be completed on an ongoing basis. CRF entries and corrections will only be performed by study site staff, authorized by the investigator. Entries and corrections to the CRF will be made following Good Documentation Practices.

The CRF will include the following information, including but not limited to: inclusion / exclusion criteria, whether patient consent obtained before start of study, demographic information, device readings, and if occurrence of any adverse event, protocol deviation, and device deficiencies, etc. The CRF will be signed by the PI and forwarded to Masimo.

CRF entries will be checked by study monitor and any errors or inconsistencies will be queried to the site on an ongoing basis. Query resolution will be assessed and confirmed by study monitor during site visit.

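### Do enrolment-based counts leave the study short when a subject exits without four valid pairs?

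*Combined protocol and SAP*

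**What the plan says.** Three operating counts use enrolment wording.

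- Section 5.1: "A minimum of 85 subjects with diversified demographics (i.e. age, gender, ethnicity, comorbidities etc.) will be enrolled".
- Section 3, on moving between stages: "Stage 2 will begin after the minimum subjects have been enrolled in the study to meet the blood pressure distribution requirements".
- Section 7.1.4, on arm circumference: "Subjects may be removed from the study as screen failures if their arm circumference falls into a bin that has had sufficient enrollment".

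In Stage 1, enrolment comes before the paired readings. Section 7.1.3 says "Subjects must meet the blood pressure requirements in order to be enrolled in the study", and this is judged on a screening pressure. Section 10.3 asks for a case report form for each enrolled subject and adds "This also applies to those subjects who fail to complete the study", so non-completers are still enrolled subjects.

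Section 3 pairs device and observer readings "for a total of 4 successful paired measurements per subject". Section 7.2.11 sets the effort: "Repeat 7.2.5-7.2.10 until at least four valid automated and auscultatory measurement pairs have been performed or eight measurement pairs have been attempted". Section 7.2.12 then ends participation for anyone still below four, and says nothing about counting or replacement.

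Section 8, the sample-size section, uses different terms. It says at least 85 subjects are required, leaves sample size and analysis wholly to ISO 81060-2:2018, and commits to following the distributions for blood pressure, gender and arm circumference.

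**The concern.** Read literally, a subject who exits under section 7.2.12 has been enrolled and so fills a place among the 85, in the blood pressure distribution and in an arm bin, without supplying a full set of pairs. A site that stopped at exactly the enrolled minimum could finish with fewer than 85 four-pair subjects, or below a required share in one category.

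The Stage 2 switch looks the most exposed. Site 1 recruits on a history of high or low pressure in Stage 1, but section 5.2 then says "Stage 2 only: No criterion for blood pressure". Site 2 is limited to subjects below 140/90 mmHg in both stages. A hypertensive subject lost around the switch would have to be made up at Site 1, whose entry criteria no longer steer recruitment that way.

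The use of one to three valid pairs also seems open. Section 5.6.2 allows analysis of data collected before withdrawal, but section 7.2.12 does not call its exit a withdrawal.

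**Working it through.** **The plan's own figure.** The 85 cannot be re-derived: the documents give no power, standard deviation or non-completion rate and refer to the standard. Only the implied total can be checked: 85 × 4 = 340 valid pairs.

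**Chance of an exit.** Inputs from section 7.2.11: four valid pairs needed, eight attempts allowed. Assumed, because the documents give no rate: each attempt is valid with probability p, independently. Then q = P(Bin(8, p) ≤ 3). For p = 0.8 the terms for 0, 1, 2 and 3 valid pairs are 0.000003 + 0.000082 + 0.001147 + 0.009175 = 0.01041. To allow for failures clustering within subjects, q was also computed from a beta-binomial with mean p and assumed correlation 0.1 (α + β = 9).

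**Consequences.** Expected losses among 85 are 85q. The chance of fewer than 85 four-pair subjects, if enrolment stops at exactly 85, is 1 − (1 − q)^85. Expected extra subjects, if each loss is replaced until 85 are complete, are 85q/(1 − q).

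| Attempts | p | q | Losses of 85 | P(<85), stop at 85 | Extras if replaced |
|---|---|---|---|---|---|
| Independent | 0.9 | 0.04% | 0.04 | 3.6% | 0.04 |
| Independent | 0.8 | 1.04% | 0.9 | 58.9% | 0.9 |
| Independent | 0.7 | 5.80% | 4.9 | 99.4% | 5.2 |
| Clustered | 0.9 | 1.04% | 0.9 | 58.8% | 0.9 |
| Clustered | 0.8 | 4.64% | 3.9 | 98.2% | 4.1 |
| Clustered | 0.7 | 12.2% | 10.4 | >99.9% | 11.8 |

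The large percentages in the fifth column apply only if recruitment halts at the floor and nobody makes up a known loss. They give the chance of missing by at least one subject, not the size of the miss.

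**Effect on precision.** The standard error of a mean over subjects scales as 1/√n. At p = 0.7 with independent attempts, 85 − 4.9 = 80.1 subjects remain and √(85/80.1) = 1.03, a 3% wider standard error. In the worst clustered case, 85 − 10.4 = 74.6 and √(85/74.6) = 1.07.

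**Arm-size halves.** Figure 5 asks for 40% of subjects in each half of a cuff's range. Assume n subjects on a cuff, m of them in the half, independent attempts and no refill. The chance that the half ends below 40% of the remaining four-pair subjects is:

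| n, m | p = 0.9 | p = 0.8 | p = 0.7 |
|---|---|---|---|
| 25, 10 | 0.4% | 9.8% | 37.2% |
| 25, 11 | 0.0% | 0.5% | 6.6% |
| 28, 14 | 0.0% | 0.0% | 0.04% |

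One spare subject removes most of the risk. No figure can be given for blood pressure categories because Figure 4 is not shown.

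**Reading the sections together.** The enrolment wording is tied to results. Stage 2 starts once enough are enrolled to meet the blood pressure distribution, section 7.1.4 speaks of sufficiency without a number and makes removal optional, and section 5.1 is a minimum. With section 8, a count that leaves the distributions unmet has not reached its stated purpose. Nor is the loss hidden: the coordinator confirms each pair's validity (section 7.3.4), and data are checked for completeness after upload (section 10.4).

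**The case for a change.** The strongest opposing case is that a floor permits more subjects but does not demand them. A site that enrols exactly 85 complies with section 5.1, section 8 does not define whether its required subjects must have four pairs, and it cites no clause for section 7.2.12 exits. Clustering is plausible because arm, cuff and observers stay the same across attempts, and even at 90% validity it raises the chance of a shortfall from 3.6% to about 59%. A sentence of clarification would cost little.

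Some of this stands. The wording is incomplete, and no readable passage settles replacement. But the harm needs someone to treat a minimum as a stopping point, know that subjects are incomplete, and submit distributions the plan says it will follow. After the Stage 2 switch Site 1 drops its pressure criterion but does not bar hypertensive or hypotensive subjects, so a lost category can still be refilled.

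On partial data, section 5.6.1 gives an open list of withdrawal reasons that includes not meeting protocol requirements. A section 7.2.12 exit plausibly fits, and section 5.6.2 would then cover the one to three pairs. The text does not say so outright.

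Replacement also has a limit: it restores the count, but not the information lost if hard-to-measure subjects are the ones who exit.

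**Conclusion.** No change follows. This is an unwritten counting and replacement policy that the sponsor can be expected to fill sensibly, since section 8 fixes the target and every loss is visible at the visit. The likely cost is small: about 0.04 to 5.2 extra one-visit subjects with independent attempts at 90% to 70% validity, or 0.9 to 11.8 with correlation 0.1. Leaving losses unreplaced would widen the standard error of the mean by 7% at most in these scenarios.

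The validity rates, the correlation and the cuff group sizes are all assumptions. At 70% validity or below the number of exits becomes material, but such a rate would show early and could be met by further recruitment. Parts of section 3 are redacted and the standard was not available, so a rule may already exist there; the most that can be said is that none is readable.

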5 SUBJECT SELECTION AND WITHDRAWAL

5.1 Number of Subjects

A minimum of 85 subjects with diversified demographics (i.e. age, gender, ethnicity, comorbidities etc.) will be enrolled.

5.2 Inclusion Criteria

- Age 18 years and older
- Site 1; Stage 1 only: Subjects with a history of hypertension ($> 140/85$ mmHg) or hypotension ($\leq 100/60$ mmHg) within the last 3 months. Stage 2 only: No criterion for blood pressure
- Site 2; Stage 1 and 2: Subjects with systolic blood pressure $< 140/90$ mmHg.
- Ability to provide informed consent

5.3 Exclusion Criteria

- Febrile subjects
- Subjects displaying respiratory symptoms, or with suspected respiratory illness
- Subjects whose skin is not intact, e.g. wounded, in or at the vicinity of the cuff placement site
- Subjects with removed axillary lymph nodes or mastectomies
- Subjects with peripheral artery disease
- Pregnant women (patient reported)
- Subjects deemed not suitable for the study at the discretion of the investigator

5.4 Study Timelines

Study participation is expected to last approximately 1 – 2 hours including the informed consent and screening procedures.

5.5 Subject Recruitment and Screening

Subjects will be recruited from the physician's practice and from a database of past volunteers. Potential subjects may be contacted by the site staff by phone using an IRB-approved phone script. Once a potential subject agrees to participate in the study, or sees the recruitment material (i.e. advertisement) and contacts the site, an appointment will be scheduled for the subject.

Subjects will be screened to determine eligibility for study enrollment. All subjects screened will be documented on the Screening and Enrollment Log. Subjects who do not meet the eligibility criteria will be considered screen failures and the reason for the status of screen failure will be documented on the Screening and Enrollment Log.

5.6 Withdrawal of Subjects

5.6.1 Informed consent documents and discussions will explicitly include emphasis that neither subject enrollment nor subject withdrawal from the study will result in any alterations to the standard clinical care. Participants may elect to withdraw at any time without any consequences or loss of benefits to which they are entitled. The subject may be withdrawn from the study prior to expected completion for reasons such as safety concerns, failure to protocol requirements, subject consent withdrawal, etc.

5.6.2 Any data collection until the time of subject's withdrawal may be included in the final data analysis, unless requested otherwise by the subject. Information of the subject's withdrawal should be documented in the case report forms (CRFs) and include clear documentation of the reason for withdrawal to the Sponsor.

6 STUDY DEVICES

FDA-cleared Devices:

Blood pressure cuff (for auscultatory measurement only)

Aneroid Sphygmomanometer

Dual Stethoscope

Investigational Devices:

Masimo blood pressure cuff

Masimo NIBP device

Data Collection Equipment:

Laptop computer with data acquisition software

6.1 Device Accountability

6.1.1 Receipt of Study Device

Upon receipt of the study device supplies, an inventory must be performed and the device accountability log filled out and signed by the person accepting the shipment. It is important that the designated study staff counts and verifies that the shipment contains all the items noted in the shipment inventory. Any damaged or unusable study devices in a given shipment will be documented in the study files. The investigator must notify the study sponsor of any damaged or unusable study devices that were supplied to the investigator's site.

